5.3 Biological sampling procedures

Pre-therapeutic biopsies will be taken during endoscopy/rectoscopy during examination of the tumour in the outpatient clinic. Biopsies will be sent according to local routines to the pathology department. The name of the pathology department will be registered in the CRF. At end of inclusion in the trial blocks will be collected from the different pathology departments for analysis at Sahlgrenska University Hospital.

Biopsies will be taken from the resected specimen at surgery and sent to the pathology department. Blocks will be collected at the end of the study and sent in batches to the study centre at Sahlgrenska University Hospital and University of Gothenburg. Patients that are considered complete responders after treatment will not be subject to further biopsies.

Blood samples will be collected at baseline, surgery and at each follow-up and stored according to a separate standard operating procedure. They will be sent for analysis to the study centre at Sahlgrenska University Hospital and University of Gothenburg.

5.3.1 Handling, storage and destruction of biological samples

All biopsies are sent to the routine pathology department. Blocks will be collected from the diagnostic procedure as well as when applicable from the surgical specimen.

Formalin fixed paraffin embedded biopsies will be stained according to our previously published multicolour panel (42). They may also be subject to assembly of tissue micro array prior to staining.

5.3.2. Total volume of blood per subject

The total volume of blood taken from each subject during the trial is a maximum of 50 ml per sampling and a total 200-250 ml/patient during the study.

5.3.3 Biobank

All samples taken in this trial, covered by the Biobank Act are registered in a biobank and handled according to the current national laws and regulations. The samples are coded to protect the subject's identity. All samples and the identification/code lists are stored securely and separately to prevent access by unauthorized persons.

5.4.1 Start of the clinical trial

The start of the clinical study is defined as the first visit of the first subject at the surgical department at any of the recruiting sites.

5.4.2 Temporary halt or early termination

The start of the study is defined as the first visit of the first subject at the surgical department at any of the recruiting sites. Sponsor will report the start of the trial through notification in the Clinical Trial Information System (CTIS) within 15 days.

The study may be prematurely terminated for safety reasons affecting the risk-benefit balance or if the recruitment of subjects cannot be completed within reasonable time. Decisions on premature termination are taken by the sponsor. The Competent Authorities should be informed as soon as possible via CTIS, but no later than 15 days after trial suspension.

503 If the study is prematurely terminated or suspended, the investigator should immediately
504 inform the subjects and ensure appropriate treatment and follow-up.

505 5.4.3 End of clinical trial

506 The trial ends when the last subject has completed the last follow-up of three years.

507 **6.0 SUBJECT SELECTION**

508 6.1 Inclusion criteria

509 To be included in the trial, subjects must meet all of the following criteria:

- 510 • The subject has given their written consent to participate in the trial
- 511 • Be 18 years or older
- 512 • Have an adenocarcinoma verified tumour within the rectum below 12 cm from anal
513 verge
- 514 • Have a tumour stage of TX/T1-3b (regardless of tumour size)
- 515 • Have no nodal metastases (NX/N0)
- 516 • Have no distant metastases (MX/M0)
- 517 • Have an Eastern Cooperative Oncology Group (ECOG) performance status 0-1
- 518 • For female subjects of childbearing potential:
 - 519 ○ Have a negative pregnancy test within 7 days prior to study entry
 - 520 ○ Agree to use adequate, medically approved, contraceptive precautions from
521 trial entry until 6 months after the end of study treatment
- 522 • If non-sterilised male with a partner of childbearing potential, must:
 - 523 ○ Agree to use adequate, medically approved, contraceptive precautions from
524 trial entry until 6 months after the end of study treatment

525 6.2 Exclusion criteria

526 Subjects must not be included in this trial if any of the following criteria are met:

- 527 • Give no informed consent
- 528 • No biopsy confirmed rectal cancer (adenocarcinoma)
- 529 • Have a recurrent rectal cancer
- 530 • An age below 18
- 531 • Have concomitant or previous malignancies within 3 years prior to trial entry, except
532 those that in the opinion of the MDT are unlikely to relapse within 3 years or lead to
533 death within 5 years
- 534 • Have unequivocal evidence of metastatic disease (includes respectable metastases)
535 (Patients with equivocal radiological lesions (e.g. retroperitoneal, liver, lung) that are
536 not classified as M1 are eligible if agreed by MDT)
- 537 • Have an MRI node positive tumour (\geq N1, defined by protocol guidelines) (Patients
538 with equivocal radiological findings that are either classified as NX or N0 are eligible)
- 539 • Have MRI extramural vascular invasion (mriEMVI) positive (defined by protocol
540 guidelines)
- 541 • Have a threatened mesorectal fascia (\leq 1 mm on MRI or ERUS)
- 542 • Have no residual luminal tumour following endoscopic resection prior to first visit at
543 surgical department

- 544 • Have contraindications to radiotherapy including previous pelvic radiotherapy
- 545 • Have uncontrolled cardiorespiratory comorbidity (includes patients with inadequately
- 546 controlled angina or myocardial infarction or arrhythmia within 6 months prior to trial
- 547 entry)
- 548 • Have known complete dihydropyrimidine dehydrogenase (DPYD) deficiency
- 549 • Have known Gilbert's disease (hyperbilirubinemia)
- 550 • Have been taking coumarin-derivative anticoagulants (e.g. warfarin) that cannot be
- 551 discontinued at least 7 days prior to starting treatment or substituted by low molecular
- 552 weight heparin
- 553 • Are taking metronidazole, phenytoin or sorivudine or its chemically related analogues,
- 554 such as brivudine, within 4 weeks of trial entry (see Section 8.3.5 for further details)
- 555 • Are Pregnant or lactating woman
- 556 • Have history of severe and unexpected reactions to fluoropyrimidine therapy

557 6.3 Screening and inclusion

558 Subject eligibility is established at the multidisciplinary meeting that often precedes the first
559 outpatient meeting after a diagnosis has been established. If the subject comes to the
560 outpatient clinic prior the multidisciplinary meeting, there is a possibility to screen for
561 inclusion and give oral and written information. This procedure is decentralized and can be
562 performed at any hospital that refers patient to any of the hospitals including in the clinical
563 trial. A member of the direct clinical care team will always make the first approach to the
564 patient.

565 The subject will then be given adequate time to consider the study and agree to participate
566 before being referred to the hospital including in the clinical trial. A treatment plan will be set,
567 and the patient will sign informed consent and can then either receive the treatment according
568 to the study protocol at the hospital participating in the clinical trial or in a decentralized
569 manner.

570 All clinical information entered into CRFs will be entered by the hospitals participating in the
571 clinical trial regardless of decentralized process or not.

572 Individuals who do not wish to enter the study will be offered standard treatment according to
573 the Swedish National Treatment Guidelines for Colorectal Cancer, i.e. TME surgery. The
574 experimental organ saving treatment is not offered outside a study setting unless unfit for
575 primary TME surgery.

576 Details of all participants approached about the trial will be recorded on the Participant
577 Screening Log. The following data will be recorded:

- 578 1. Sex
- 579 2. Age
- 580 3. Clinical TNM according to TNM v8
- 581 4. Planned oncologic and surgical treatment

582 In addition – all patients treated at the participating hospitals are registered in the Swedish
583 ColoRectal Cancer Registry (SCRCR). If necessary, missing information will be retrieved
584 (sex, age and clinical TNM stage, type of surgery performed and recurrence data) on non-
585 included patients using the SCRCR

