Exclusion criteria:	
 • MRI node positive ($\geq N1$, defined by protocol guidelines) • MRI extramural vascular invasion (mriEMVI) present (defined by protocol guidelines) • MRI defined mucinous tumour • Mesorectal fascia threatened by tumour (≤ 1 mm on MRI or ERUS) • Maximum tumour diameter >40 mm (either measured from everted edges on sagittal MRI or ERUS examination) • No residual luminal tumour following endoscopic mucosal resection or similar local excision • Prior pelvic radiotherapy • Definite evidence of regional or distant metastases (M1) in opinion of MDT • Uncontrolled cardiorespiratory comorbidity (inadequately controlled angina or myocardial infarction or arrhythmia within 6 months prior to trial entry) • Known complete Dihydropyrimidine Dehydrogenase deficiency • Known Gilbert's disease • Medication with coumarin-derivative oral anticoagulants that cannot be stopped or substituted by low molecular weight heparin • Medication with metronidazole, phenytoin, sorivudine or its analogues, such as brivudine • Pregnancy or breast feeding • Age <18 years
Intervention:	
This is a low intervention trial as the investigational medicinal product (Capecitabine) is already authorized, used according to the terms in its marketing authorization to the same diagnosis but at a different tumour stage than standard and the complementary diagnostic procedures do not contribute to the risk or burden to subject safety compared to normal clinical practice.
 
Patients will choose organ preservation or standard surgery. Those who prefer organ preservation will be treated with mesorectal CRT
 
Those who prefer standard surgery or have no preference, will undergo standard TME surgery without neoadjuvant treatment. They will be asked to participate in the QoL part of the study, while the remainder of the data will be extracted from the national quality registry, the Swedish ColoRectal Cancer Registry (SCRCR)
 
Long course concurrent chemoradiation (CRT): Capecitabine: 825 mg/m² orally, b.d., on radiotherapy days Radiotherapy: A dose of 50 Gy applied to the primary tumour and surrounding mesorectum in 25 fractions of 2 Gy, 5 days a week.

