The STAR-TREC trial included patients with a radiological staging Magnetic Resonance Imaging (MRI)-stageTX/T1-3b, NX/N0, MX/M0 rectal tumour. Exclusion criteria were designed to avoid including patients with known risk factors for locoregional relapse following rectal cancer treatment. This study will use the same inclusion criteria, and similar follow-up routine. Patients who choose standard treatment i.e. radical surgery (TME-surgery) will be the control arm.

The choice to refrain from local surgical resection of a possible small regrowth or insufficient response lies in a combination of clinical observations of morbidity and insufficient clinical experience at the study sites. It may be reconsidered when the long-term results from the STAR-TREC study are available, and the use of local excision is supported by the recent data from the TAUTEM trial where mesorectal CRT and TEM were found non-inferior to standard TME resection (36).

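### Synopsis and section 6 define two incompatible populations: the synopsis excludes tumours over 40 mm and mucinous tumours, section 6 sets no size limit and omits mucinous type, and neither list is given precedence

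*Protocol*

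**What the plan says.** **Synopsis, exclusion criteria.** Two of the listed exclusions are "Maximum tumour diameter >40 mm (either measured from everted edges on sagittal MRI or ERUS examination") and "MRI defined mucinous tumour".

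**Section 6.1, inclusion criteria.** The list opens with "To be included in the trial, subjects must meet all of the following criteria". Its stage criterion is "Have a tumour stage of TX/T1-3b (regardless of tumour size") and its nodal criterion is "Have no nodal metastases (NX/N0").

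**Section 6.2, exclusion criteria.** The list opens with "Subjects must not be included in this trial if any of the following criteria are met". It contains no diameter limit and does not mention mucinous tumours.

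**Section 2.4.** Referring to STAR-TREC, it says: "This study will use the same inclusion criteria, and similar follow-up routine". It reproduces that trial's stage criteria only and gives no size or mucinous rule.

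**Use of the population.** Sections 4.3 and 8.1.1 define the primary endpoint as the proportion with cCR at one year among patients who start on the non-operative route. Section 4.0 sets the target at 50% or more. Section 10.1 gives the decision rule: 82 patients, with rejection of the null at 49 or more responders.

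**The concern.** Both lists are written as the eligibility criteria of the trial. A patient with a T2 N0 tumour of 45 mm who meets everything else is ineligible under the synopsis and eligible under section 6. Nothing in the protocol tells a site which list to follow.

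This matters for two reasons. First, eligibility decides who may be offered chemoradiotherapy as an alternative to upfront total mesorectal excision (TME). Second, the primary test has no randomised comparator, so the cCR proportion can be interpreted only for a stated population. Section 2.4 gives comparison with other studies as a purpose, which also needs a population that can be named. Screening may take place at any referring hospital (section 6.3), which leaves room for different readings. The screening log records sex, age, TNM and planned treatment. T category is defined by depth of invasion, so the log would not show afterwards which patients only one list would have admitted.

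**Working it through.** **1. The two lists side by side**

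| Item | Synopsis | Section 6 | Type of difference |
|---|---|---|---|
| Maximum diameter | Above 40 mm excluded | Any size admitted (6.1); no limit in 6.2 | Direct conflict |
| Mucinous on MRI | Excluded | Not mentioned in 6.1 or 6.2 | Conflict by omission |
| T category | Inclusion bullet T1-3b (printed with a doubled T) | TX/T1-3b | Lesser; the bullet may be a typing error |
| N category | Inclusion bullet N0, but the population row gives Nx/N0 | NX/N0; 6.2 also accepts equivocal nodes classed NX or N0 | Lesser; the synopsis disagrees with itself |
| MDT finds both TME and chemoradiotherapy suitable | Explicit criterion | Not listed; 6.3 places eligibility at the MDT meeting | Lesser; the step remains, the explicit test does not |

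The first row cannot be explained by abridgement. A synopsis may leave detail out, but here it is the stricter text, and section 6.1 expressly removes the limit that the synopsis imposes.

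**2. Can another part of the protocol settle it?** No. Neither the 40 mm limit nor mucinous type appears anywhere else in the text supplied. Sections 2.4 and 4.0 point to STAR-TREC but give no rule on either item.

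**3. The plan's own decision rule**

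Inputs: n = 82 and critical value 49 (section 10.1); null rate 0.50, inferred from section 4.0 because section 10.1 does not state it; alpha 0.05 with sidedness not stated.

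Exact binomial tails at a true rate of 0.50:
- P(X ≥ 49) = 0.0485
- P(X ≥ 48) = 0.0753

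So 49 is the smallest critical value that keeps a one-sided test at or below 0.05. Doubling the tail gives 0.097, so the rule fits only a one-sided test. The rule reproduces, and its arithmetic does not depend on which eligibility list applies.

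**4. Illustration of how the mix could act**

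Section 2.4 reports 57% cCR at one year with chemoradiotherapy in STAR-TREC. At a true rate of 0.57, P(X ≥ 49 of 82) = 0.349.

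Let *s* be the share of patients whom only section 6 admits and *q* their cCR rate. Neither is in the documents; both are assumed. The overall rate is p = 0.57(1 − s) + q·s.

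| s | q | p | P(X ≥ 49 of 82) |
|---|---|---|---|
| 0.10 | 0.20 | 0.513 + 0.020 = 0.533 | 0.144 |
| 0.10 | 0.30 | 0.513 + 0.030 = 0.543 | 0.189 |
| 0.10 | 0.40 | 0.513 + 0.040 = 0.553 | 0.243 |
| 0.20 | 0.20 | 0.456 + 0.040 = 0.496 | 0.042 |
| 0.20 | 0.30 | 0.456 + 0.060 = 0.516 | 0.085 |
| 0.20 | 0.40 | 0.456 + 0.080 = 0.536 | 0.157 |
| 0.30 | 0.20 | 0.399 + 0.060 = 0.459 | 0.008 |
| 0.30 | 0.30 | 0.399 + 0.090 = 0.489 | 0.032 |
| 0.30 | 0.40 | 0.399 + 0.120 = 0.519 | 0.094 |

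If *q* equalled 0.57, the mix would have no effect at all. The table shows how the mechanism works; it does not estimate its size in this trial.

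**The case against.** The best defence is that section 6 is a complete operative list with binding wording, so sites will follow it and the synopsis is merely out of step. That may happen, but the protocol does not say so. The synopsis list is worded as eligibility criteria too, and it is the stricter one.

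Several stronger readings are tempting, and the documents do not support them:

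- **That the population is undefined.** Each list on its own defines a population. The defect is that there are two, they are incompatible, and none has precedence.
- **That the protocol itself shows size or histology drives response.** Section 2.2 ties response to T stage. It says nothing on diameter or mucinous type, and both lists stop at T3b. An effect of size on cCR is an assumption here.
- **That surgery would be withheld from some patients.** Patients choose. Those who prefer surgery or have no preference have upfront TME (section 5.1).
- **That the synopsis admits N0 only, or that section 6 has dropped the MDT.** The synopsis population row includes Nx, and section 6.3 keeps an MDT eligibility step. Section 6.2 also excludes contraindications to radiotherapy.
- **That section 2.4 proves one list wrong.** It speaks of inclusion criteria and reproduces stage only, which section 6.1 matches. Whether either list agrees with STAR-TREC on size or mucinous type cannot be checked here.
- **That the conflict costs a known amount of power.** The low starting probability of 0.349 at 57% is there under either list, the synopsis says that the number of patients is not fixed, and every further drop comes from assumed values.

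It is also fair to say that the variable list (Appendix B) is not shown, so diameter and mucinous status may already be collected. None of this removes the direct conflict on size or the missing mucinous criterion.

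**Conclusion.** The point stands as an internal contradiction that must be corrected before the first patient is included. Size is contradicted outright, and mucinous type is excluded in one list and absent from the other. The TX/NX and MDT differences are secondary and should be tidied at the same time.

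This conclusion rests on the text alone and needs no numerical assumption. The size of the effect on the cCR result cannot be obtained from the documents. The figures above depend wholly on assumed shares and response rates, and on an inferred one-sided null of 50%. An SAP cannot repair the conflict, because it acts after patients have been enrolled. Which criteria are right is a clinical decision and is not judged here.

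**What to change.** - Before first inclusion, make the synopsis and sections 6.1 and 6.2 one identical list covering maximum diameter, mucinous type, TX/NX and the MDT criterion. The clinical leads decide which criteria stand.
- Record maximum diameter and MRI mucinous status at baseline if Appendix B does not already do so.
- If the wider population is kept, report the primary endpoint overall and also in the subset that meets the synopsis criteria, unless the SAP already provides for this.

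The cost is a text correction, through a protocol amendment where one is required, and at most two baseline fields that can be taken from the staging work-up. If the stricter list is chosen, accrual may be somewhat slower.

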6.4 Withdrawal criteria

Subjects can discontinue their participation in the study at any time without any consequence to his/her continued treatment. The investigator/sponsor can at any time terminate the study for a subject due to, e.g., unacceptable adverse events/adverse reactions or because the subject does not follow procedures in the clinical trial protocol. If the subject discontinues the trial, follow-up of this subject will be performed according to the clinic's routine.

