7.4 Surgery

If the patient does not achieve complete response after the second evaluation after neoadjuvant treatment surgery will be recommended. Any deviation from this will be considered a protocol violation and must be registered. It is important that the patient understand that there is an increased risk of tumour progression if surgery is not performed at this stage.

The preoperative and perioperative treatment regarding anaesthesia and antibiotics and all other details must follow local guidelines.

All patients should be given pre-operative prophylactic antibiotics and antithrombotic medication such as low molecular heparin before the start of the operation. The type of antithrombotic medication should be registered in the eCRF. Any bowel preparation performed is according to local/regional/national routine. For the purpose of this study TME surgery is defined as previously published (44). No distinction is made between different surgical approaches. Laparoscopic, robot assisted laparoscopy, or open surgery can all be used and the choice is at the discretion of the surgeon.

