9.0 HANDLING OF ADVERSE EVENTS

NOTE! In this study the following events are not reported as an AE or SAE:

- Planned surgery (e.g. TME surgery or stoma reversal)
- Planned hospitalization
- Recurrence
- Death due to progression of the disease

Any adverse events (AE) and serious adverse events (SAE) will be reported during the trial during the first year.

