9.2.2 Assessment of intensity

Patients should be reviewed at least weekly during CRT to perform an assessment of acute toxicity. Remote toxicity assessments (e.g. over the telephone) are allowed as per local practice 4. The local team should have a structure in place that ensures that patients experiencing side effects can be seen and undergo review.

The following guidance should be followed for the management of acute toxicity and dose modifications:

- Adverse Events (AEs) should be graded according to the NCI Common Terminology Criteria for Adverse Events version 4.03 (CTCAE v4.03)
- In the event of overlapping toxicities, dose modification should be based on the worst toxicity grade observed.
- All dose modifications should be documented with clear reasoning and documentation of the approach taken in the CRF and in the medical notes.
- If a patient experiences a toxicity, then dose modifications should be applied as specified in the protocol section 8.3.7.
- **In the event of a second episode of the same grade ≥ 3 toxicity, capecitabine should be permanently discontinued.**

Dose modification and toxicity should be managed according to local routines. Details on toxicity is registered in CRF.

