9.4 Follow-up of Adverse Events

All adverse events will be followed until they have abated, or until a stable situation has been reached. Depending on the event, follow up may require additional tests or medical procedures as indicated, and/or referral to the general physician or a medical specialist.

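### Section 6.4 does not separate stopping study treatment from leaving the study, so the one-year response, later adverse events, quality of life and late toxicity can be missing for outcome-related reasons

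*Protocol*

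**What the plan says.** Section 6.4 of the protocol first lets subjects leave whenever they wish. It then gives the investigator and sponsor their own power: "The investigator/sponsor can at any time terminate the study for a subject due to, e.g., unacceptable adverse events/adverse reactions". Non-adherence is named as a second ground, for a removal made "because the subject does not follow procedures in the clinical trial protocol". The section closes with: "If the subject discontinues the trial, follow-up of this subject will be performed according to the clinic's routine". Nothing in 6.4 describes a patient who stops treatment but stays in the study, and nothing lists data to be collected after removal.

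Other sections bear on the same patients:

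- Section 9.2.2, on a repeat of the same grade 3 or worse toxicity: "capecitabine should be permanently discontinued". Leaving the study is not mentioned.
- Section 7.4, on not having the surgery recommended after an incomplete response at the second evaluation: "Any deviation from this will be considered a protocol violation and must be registered". Removal is not mentioned.
- Section 9.0: "Any adverse events (AE) and serious adverse events (SAE) will be reported during the trial during the first year". Section 9.3 places this registration at the trial visits, up to one year after entry.
- Section 9.4: "All adverse events will be followed until they have abated, or until a stable situation has been reached". No exception is made for removed subjects.
- Section 9.1.2 has serious adverse events reported if they occur within 30 days of stopping study treatment.

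**The concern.** Chemoradiotherapy lasts five weeks (7.1.2, 7.3.9), while outcomes are collected for three years (5.1, 8.1.2). A toxicity that justifies stopping a five-week course is no reason to stop observing the patient for the remaining years. Section 6.4 nevertheless offers ending the study as the response to an adverse event or to a departure from procedures.

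Both grounds are related to outcome. Patients removed under them will tend to differ from those who stay, in toxicity, in tumour course or in both. If their later records are missing, the remaining records describe a selected group. A statistical analysis plan can say how missing values are handled, but it cannot supply data that the protocol ceased to collect. The late-toxicity record matters here because section 2.3 says that long-term morbidity is not yet well described.

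**Working it through.** The point rests on the text. The first two steps set the sections side by side; the third asks what can be said about size.

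**Step 1: what 6.4 ends.** The object of the investigator's or sponsor's decision is the study for that subject. Sections 9.2.2 and 7.4 show that the protocol can stop a drug, or register a violation, without ending participation. Section 6.4 does not draw that line.

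**Step 2: what is kept and what is exposed after removal.**

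| Item | Source | After removal |
|---|---|---|
| Data up to removal, including the prompting event | 9.3, 9.3.1, SAE reporting in 9.3.2 | Kept |
| Course of the prompting event | 9.2.1, 9.4 | Still followed |
| Serious events within 30 days of stopping treatment | 9.1.2 | Still reported |
| Other new adverse events up to one year | 9.0, 9.3 (at trial visits) | Not secured |
| One-year MRI, clinical and endoscopic response | 4.3, 8.1.1 | Not secured |
| Quality of life at 1, 2 and 3 years | 8.1.3 | Not secured |
| Chemoradiotherapy toxicity at 24 and 36 months | 5.2, visit table | Not secured |
| Surgery and recurrence | SCRCR, 6.3 | Data exist, but retrieval is written only for non-included patients |
| Vital status | 5.1, SCRCR and Cause of Death Registry | Named only at 5 years |

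**Step 3: size.** The protocol gives no expected number of removals, so the loss cannot be calculated. Its only related figure is the decision rule in 10.1: 49 responses in 82 patients at alpha 0.05. The null rate is not stated there; 50% is assumed from section 4.0. With X ~ Bin(82, 0.50):

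- P(X ≥ 49) = 0.0485
- P(X ≥ 48) = 0.0753

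So 49 is reproduced as the smallest one-sided rejection count. A two-sided test at 0.025 per tail would need 51.

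A sensitivity illustration follows, with every k an assumption. Suppose the true rate is 50% in all 82, k true non-responders are removed and dropped from the denominator, and the critical count r is reset for m = 82 − k. The expected observed rate is 41/m, and the chance of rejecting is P(X ≥ r) with X ~ Bin(82, 0.50).

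| k | m | r | 41/m | P(reject) |
|---|---|---|---|---|
| 0 | 82 | 49 | 50.0% | 0.049 |
| 2 | 80 | 48 | 51.2% | 0.075 |
| 4 | 78 | 47 | 52.6% | 0.112 |
| 8 | 74 | 45 | 55.4% | 0.220 |
| 12 | 70 | 43 | 58.6% | 0.370 |

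If the same patients are kept and counted as non-responders, P(reject) stays at 0.049 for every k. The table shows why the one-year record of removed patients matters. It does not show an error in the plan.

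**The case against.** A reader might infer that the patients most harmed leave the safety data altogether. The documents do not support that. Adverse events enter the CRF within 72 hours and serious ones reach the sponsor within 24 hours, and 6.4 discards nothing. What is exposed is the later record, not the harm that led to removal.

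A reader might also see a flat contradiction with 9.4. There is none: 9.4 allows follow-up through a general physician or specialist, so a site can obey it alongside clinic routine. The link between the two sections is simply not written. Nor does 6.4 defeat 7.4, which registers patients who do not have the recommended surgery and says nothing of removing them. Section 6.4 only permits removal.

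The wording of 6.4 leaves a further opening. It uses one verb for the subject's own choice (to discontinue) and another for action by the investigator or sponsor (to terminate). The clinic-routine sentence uses the first, so it could be confined to voluntary withdrawal. That reading is possible. On it, however, 6.4 says nothing about follow-up after removal by the investigator or sponsor, and the collection is still not secured.

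Progression and later surgery are not simply lost either, because patients treated at participating hospitals are in the SCRCR. What is missing is a statement that it will be used for removed participants, and no section says that it holds toxicity, quality of life or one-year response. The absence of a safety committee (9.5) adds little, since independent monitoring, sponsor SAE reporting and annual safety reports remain.

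**Conclusion.** The concern holds in a limited form. Section 6.4 merges stopping treatment with leaving the study, and on its natural reading ends protocol follow-up for two reasons related to outcome. New adverse events up to one year, the one-year response, quality of life and the 24- and 36-month toxicity records can then be missing selectively. This should be corrected, because the analysis cannot repair it later.

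No size can be given. One might apply the 57% one-year response reported for STAR-TREC to 82 patients, 0.43 × 82 = 35.3, and take a share of these as refusing surgery. That base is wrong: it includes patients who lost their response later, whereas 7.4 concerns those without a complete response at the second evaluation. The share itself would be a guess, and the synopsis leaves the number of patients open. One might also infer an inflated false-positive rate from the illustration. That depends on removed patients being dropped from the denominator. The endpoint's base in 4.3 is all patients with a non-operative approach at onset, and the analysis plan, which is not shown, may count removed patients as failures.

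**What to change.** Reword 6.4 to say that adverse events, stopping treatment or deviating from procedures do not by themselves end study follow-up. The planned safety collection, the one-year endpoint assessment and the 1-, 2- and 3-year CRF data should continue for every included patient who chose organ preservation, whether or not chemoradiotherapy was started or completed, unless the patient withdraws consent to data collection. This matches the endpoint's base in 4.3; limiting it to patients who started treatment would not.

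For patients who stop attending visits, state that surgery, recurrence and vital status will be taken from the SCRCR and the Cause of Death Registry, within the consent given. Cross-refer 6.4 to 7.4, 9.1.2, 9.3 and 9.4 so that the sections agree. No rule on when treatment is stopped or surgery advised needs to change.

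The cost is a few sentences in the protocol, a matching line in the patient information, and some continued data collection for patients who would otherwise have been removed. No visits are added beyond those already planned.
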